### Lay Summary

The purpose of this study is to employ ecological momentary assessment (EMA) methods to evaluate the impact of suvorexant on alert cognition and daytime symptoms among community-dwelling older adults with insomnia.

Traditional assessment methods such as retrospective questionnaires or standard neurocognitive tests enable measurement of symptoms at one point in time, in a research environment. By contrast, remote monitoring approaches such as ecological momentary assessment (EMA; e.g., administered via mobile device) enable ongoing, data-rich assessment of symptoms such as cognitive alertness, fatigue, and low mood in participants' natural environments.

### Specific Aims

The long-term goal of this research is to improve outcomes for patients with sleep disorders. The overall objective of the current application is to test preliminarily remote monitoring and ecological momentary assessment (EMA) methods for measuring the impact of insomnia treatment on daytime symptoms (i.e., to employ EMA as an outcome measure). Based on prior research, our central hypothesis is that relative to placebo, suvorexant improves daytime insomnia symptoms as assessed via EMA.

Specific Aim 1: To employ ecological momentary assessment (EMA) methods to evaluate the impact of suvorexant on daytime insomnia symptoms among community-dwelling older adults with insomnia.

Hypothesis 1: Relative to placebo, suvorexant improves alert cognition and daytime symptoms as assessed via EMA.

### Design

This is a single-site, double-blind, randomized, placebo-controlled clinical trial. The study employs a two-group (suvorexant, 20mg, qhs, versus placebo) parallel design and involves remote (baseline) assessments, 16-day active treatment phase with intensive ambulatory monitoring via wrist actigraphy and ecological momentary assessment (EMA). Outcome

assessments are conducted at two weeks while participants are on study treatment or placebo and include self- report questionnaires and comprehensive cognitive testing administered by computer.

## **STUDY PROCEDURES**

### **Recruitment**

Participants will be recruited to the study in several ways (i.e., volunteer lists, mailings based on EPIC searches, newspaper advertisements, online and social media advertisements, public presentations, and word of mouth and study fliers at the University of Maryland Sleep Disorders Center, Midtown Campus). Approaches to recruitment are described in “Recruitment” section below.

#### **Self-Screening Form Process**

In all recruitment pathways except for online and social media advertisements, the participants will be provided with study staff contact information, and the participant will call (or video chat, if requested) with study staff to be screened for the study. For online and social media, advertisements, and recruitment pathways, the participants will be provided with study staff contact information. If interested in the study, the participant will complete an online preliminary screening questionnaire prior to being phone-screened. If individuals meet the initial study criteria via preliminary screening, then the information will be sent to the recruitment team for review before contacting the participant via phone.

#### **Phone Screening**

Interested participants will speak remotely e.g., over the phone or via secure teleconferencing platforms like Zoom with study staff to confirm high likelihood of insomnia and low risk for major untreated medical, psychiatric, and other sleep disorders. This screening will assess all eligibility criteria (e.g., age, sleep difficulties, substance use, existing medical conditions) in addition to confirming that the volunteer will be available locally during the course of the study (i.e., confirming that the volunteer will not be traveling during the duration of the study). Individuals who pass the initial screening will be invited to complete remote assessments with trained project staff to confirm eligibility for the study. Given that participants will be older adults, project staff will provide technical assistance whenever possible.

#### **Eligibility/Consenting/Phone Call**

Participants will receive the study consent form via email (or via snail mail if requested). The study team will work with potential participants to complete the informed consent process. Participants will provide their signed consent to participate in the study. Once signed consent is confirmed, participants will complete the remote assessments. Then the study staff will confirm eligibility and the sleep expert (i.e., PI) will confirm individual's study participation.

Once study participation is confirmed, the participant will be randomized to drug or placebo in a 1:1 ratio by the IDS pharmacy. Throughout the study participants will wear an actigraph. An actigraph is a wristwatch-like device that detects ambulatory movement, a validated proxy for sleep. Participants will also complete brief surveys four times per day for 16 days. At post-treatment, participants will complete validated questionnaires, neurocognitive tasks, and a brief satisfaction survey. Additional details presented below.

### **Remote Assessments (Day 0)**

Study staff will schedule a time for participants to complete the remote assessments. These include a semi-structured interview, validated questionnaires (about 45-60 minutes), and computerized neurocognitive tasks (about 15-20 minutes). Participants will complete the remote assessments over one day (90 minutes) or two days (about 45 minutes each day). For participants who prefer to complete the remote assessments over two days, the first day will include the consent and interview. The second day will include the validated questionnaires and neurocognitive tasks.

Participants use a special research smartphone app for this study, which will capture daily surveys (described below). All study tasks will be remote, e.g., over the phone or via secure teleconferencing platforms like Zoom. During the remote assessments, participants will have many breaks to help them stay refreshed. Participants can also request a break after any task.

Neurocognitive tasks are computerized measures that include the psychomotor vigilance test (PVT), Stroop Task, and a Task-switching exercise developed for use among older adults. To help participants complete these tasks, study staff will email or text participants a link, which will enable completion of the computerized tasks on participants' smartphone, laptop, or desktop computer. In the tasks participants will be asked to respond to words, shapes, and colors on their screens.

### **Home Sleep Apnea Test (Day 0)**

Participants will complete a Home Sleep Apnea Test (HSAT) early in the study to evaluate their breathing during sleep. The HSAT will determine if participants have obstructive sleep apnea (OSA). The HSAT device will be mailed to participants by a third-party company supporting this study. Participants will follow instructions on how to use the device. Participants will return the device using a pre-paid return mailing envelope. Participants will have 24-hour support if needed.

### **Actigraphy Setup (Days 1-16)**

Once participants complete the remote assessments participants will set up their actigraph with study staff. Study staff will contact participants to review instructions and inquire of general questions of quiet time activities remotely e.g., over the phone or via secure teleconferencing platforms like Zoom. Participants will be instructed to wear an actigraph on their non-dominant hands for approximately 16 days. We will mail participants an actigraph along with a pre-paid mailing envelope. Actigraphs are expensive

research devices and must be returned. Study staff will call to remind participants when it is time to return the actigraph.

### **Daily Survey Completion (Days 1-16)**

While participants wear the actigraph, they will also complete brief surveys on their mobile phones. The surveys are sent to participants 4 times a day for 16 days. Each survey takes less than 2 minutes to complete. Participants' phones will send them notifications for each survey. At the start of the study, participants will choose what time they want surveys to start. Every morning, participants will complete a survey that includes a brief sleep diary and questions about generalized quiet time activities and how they feel. Next, participants will complete three more surveys throughout the day. These surveys also ask about how they feel. These surveys will be given at random times throughout the day, about two hours apart over the next 12 hours. Study staff will be available to answer any questions or give support. Contact information for study staff and technical support will be given to them.

### **Post Assessments (Prior to Day 16)**

Study staff will schedule a time for participants to complete the post-assessment before discontinuing study drug or placebo. These assessments include validated questionnaires (about 45-60 minutes), computerized neurocognitive tasks (about 15-20 minutes), and a brief satisfaction survey

### **Unique Identifiers**

Study staff will assign each participant a unique 4-digit identification number, generated by an online random integer generator. Any information linking the subject ID to PHI will be kept in the master/coded list, which will be stored virtually in a limited access, password-protected drive on UMB-encrypted devices. The folder with all participant PHI will be accessible only to trained study staff authorized by the PI to access these files.

### **Neurocognitive Testing**

General neurocognitive function will be assessed by using computerized testing which can be completed via a software package developed specifically for remote administration. Measures to be administered include sustained attention (psychomotor vigilance task [PVT]), inhibition (Stroop task), and task-switching/executive function (task-switching task). Participants will receive a link to complete the neurocognitive tasks. These tasks can be completed in approximately 15-20 minutes via smartphone, laptop, or desktop computer. It should be noted that no PHI will be entered or transmitted, participants will be identified using only a participant ID.

### **Training in EMA and Actigraphy**

Participants will be trained on how to use a secure mobile app, like RealLife Exp (by LifeData), which includes ecological momentary assessment (EMA) functionality. App versions for iOS and Android are available. As indicated above, participants will also be instructed on the proper use of a research actigraph and provided such device via tracked mail (e.g., FedEx) specific registration and data coding procedures are presented below:

1. Participants will be provided an actigraph, in addition to receiving training in using the mobile app.
2. Participants will be provided a reminder card as well as contact information for the study staff, should any questions arise during the study.
3. Trained study staff will instruct participants in detail regarding each step of the study, so that participants always know what to expect.

### **Insomnia Treatment-Suvorexant (FDA-Approved)**

All packaging label-insert instructions and guidelines will be followed at all times during this study.

Eligible participants will be initiated on 10mg suvorexant (or placebo), po, qhs, including instructions on dosage, expectations, and potential side effects. Following this two-day period, individuals in the treatment condition will be increased to 20mg for a 14-day active treatment period (i.e., 16 nights taking a pill).

Individuals in the control condition will continue with placebo (16 nights taking a pill). Consistent with the Model Study Agreement and UMMC IDS Pharmacy policies and procedures, robust safety measures will be followed and, study staff will contact the participant after starting Suvorexant (or placebo).

### **Home Sleep Apnea Test (HSAT)**

All eligible participants will undergo HSAT to evaluate sleep-disordered breathing. HSAT will be administered by a third-party provider, CleveMed. For individuals recruited from various sleep disorders center (including those who already have an OSA diagnosis and use a CPAP device) will have previously been referred for overnight polysomnography (PSG) or HSAT as part of their routine clinical care. These individuals may not be required to complete an HSAT; with participant consent, the presence of OSA for this study will be based on clinical PSG (or HSAT) findings.

## **SAMPLE SIZE AND DATA ANALYSIS**

### **Sample Size**

The DISS will serve as our primary endpoint, and the power/sample size analysis is based on this primary endpoint. Our mixed model approach depends on the size of the intra class correlations (ICC) between repeated measures. Based on results from our prior research), with a sample size of 20 completers each arm and 20% attrition rate, we would have the power of 0.92 to detect a medium effect size of Cohen's  $d=0.5$  based on simulation analysis at the  $\alpha$  level of 0.05. Given the measurement sensitivity of our approach, we anticipate sufficient power to detect differences between groups for both cognitive and sleep outcomes.

Multiple corrections will be performed at the critical p-values of 0.05, 0.025, and 0.017 to show minimum and maximum sensitivities using the false discovery (FDR) method, which

is contingent upon the number of outcome measures that exceed these given critical values.

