#### Main Analysis

The Primary Endpoint (PE) is the between-group difference (SUV vs PBO) in each DISS subscale at four EMA time-of-day assessments (Morning, Midday, Afternoon, Evening) across the study period. Based on our current MISP, we anticipate high adherence with >80% completion of all assessments. We will fit linear mixed-effects models for each subscale, including fixed effects for Group, Time of Day, Day (1–16 continuous), age, and sex; and a random intercept for each participant. The Group×Time interaction will be evaluated using a 4-degree-of-freedom Wald test to determine whether suvorexant and placebo differ at any time of day. If needed, the generalized additive model (GAM) will be used to account for the non-linear time effects. Covariates will be limited to age and sex at birth. Multiple imputation will be implemented for missing data; to confirm the assumptions of multiple imputation that data is missing at random, we will perform sensitivity analyses.

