#### Secondary Analyses

To examine the effects of treatment with each secondary EMA endpoint including fatigue/sleepiness, positive affect, and negative affect, we will employ the model described above (i.e., same approach as used in the primary analysis). To examine the effects of treatment on 1) sleep continuity variables (sleep onset latency, wake after sleep onset, sleep efficiency, and total sleep time) as measured by sleep diary and actigraphy, 2) self-report questionnaires, and 3) cognitive testing, scores will be compared both within and between-groups adjusting for baseline values using analysis of covariance (ANCOVA). This procedure is known to maximize power.

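### The primary test is named as an interaction (3 df) but specified as a joint test (4 df), and the power of 0.92 is not tied to either

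*Combined protocol and SAP*

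**What the plan says.** **Primary test (Main Analysis).** The primary endpoint "is the between-group difference (SUV vs PBO) in each DISS subscale at four EMA time-of-day assessments". A separate linear mixed model is fitted for each subscale, "including fixed effects for Group, Time of Day, Day (1–16 continuous), age, and sex", with a random intercept per participant. Then: "The Group×Time interaction will be evaluated using a 4-degree-of-freedom Wald test" "to determine whether suvorexant and placebo differ at any time of day".

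**Hypothesis (Specific Aims).** "Relative to placebo, suvorexant improves alert cognition and daytime symptoms as assessed via EMA". No time-of-day pattern is specified.

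**Power (Sample Size).** The DISS is treated as a single endpoint: "with a sample size of 20 completers each arm and 20% attrition rate, we would have the power of 0.92" for Cohen's d = 0.5, by simulation at alpha 0.05. The section does not give the ICC, the sidedness, the SD behind d, or the model and test that were simulated.

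**Multiplicity (Sample Size).** "Multiple corrections will be performed at the critical p-values of 0.05, 0.025, and 0.017", by a false discovery rate method that depends on the number of outcome measures. The outcome measures in the family are not listed.

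**Secondary EMA endpoints (Secondary Analyses).** Fatigue/sleepiness, positive affect and negative affect are analysed with the same model as the primary endpoint.

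**The concern.** The name of the primary test and its degrees of freedom point to two different tests, which answer different questions. The 3-df interaction asks whether the treatment effect changes over the day. The 4-df joint test asks whether there is an effect at any time of day. A steady improvement from morning to evening is fully compatible with Hypothesis 1. The joint test can find it and the interaction test cannot. Two analysts working from the same paragraph could therefore report opposite primary conclusions, and the ambiguity carries over to the secondary EMA endpoints. If it is still open at unblinding, the choice of test could be influenced by the data.

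The second issue is the link from the power figure to this test. A power for one DISS endpoint at 0.05 does not by itself give the power for each of several subscales under a correction whose scope is undefined.

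**Working it through.** **1. Degrees of freedom.** Inputs from Main Analysis: 2 groups, 4 times of day, Group already a fixed effect.
- Group×Time of Day interaction: (2−1)×(4−1) = 3 df.
- Group plus Group×Time of Day, tested jointly: 1 + 3 = 4 df. This is equivalent to testing that all four time-specific group differences are zero, which is the stated purpose.
- The listed fixed effects contain no interaction. Fitted literally, the model has one group difference common to all times, and neither test can be formed.

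**2. What the named test does with a uniform benefit.** Let D1 to D4 be the group differences at the four times. The 3-df test uses only the deviations of D1 to D4 from their mean. If all four equal δ, every deviation is zero, the noncentrality is 0 and the rejection rate is alpha, whatever δ, the ICC or n. Simulation with 20 per arm, 64 surveys each (4 × 16), ICC 0.1 to 0.7 and 20,000 replicates gave 0.048 to 0.052 at alpha 0.05.

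**3. Can 0.92 be reproduced?** Only conditionally.
- One measurement per person, n = 20 per arm, d = 0.5, two-sided 0.05: power 0.35 (0.34 by the t distribution).
- Mean of m = 64 surveys under a random intercept, d scaled to the total SD: SD = sqrt(ICC + (1−ICC)/m), power = Φ(d·sqrt(n/2)/SD − 1.96). With ICC = 0.208, SD = sqrt(0.208 + 0.792/64) = 0.469, and 0.5·sqrt(10)/0.469 = 3.37, so power = Φ(1.41) = 0.92.
- The same formula gives 0.81 at ICC 0.3 and 0.60 at ICC 0.5.

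The figure is attainable, but it cannot be checked without the ICC.

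**4. Effect of the multiplicity rule on the same test.** Assumption: the family is three primary subscales, each with power 0.92 at 0.05 (two-sided z, noncentrality 1.960 + 1.405 = 3.365). The number of subscales is not stated in the documents. Simulation, 400,000 replicates, correlation 0 to 0.9:

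| Situation | Power per subscale |
|---|---|
| All three respond, Benjamini-Hochberg (0.0167, 0.0333, 0.05) | 0.916 to 0.900 |
| All three respond, step-up at the plan's own values (0.017, 0.025, 0.05) | 0.912 to 0.895 |
| Only one responds, so it is judged at about 0.017 | 0.836 (z), 0.839 (chi-square, 4 df), 0.825 (t, 20 per arm) |

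**5. If a 1-df group comparison was simulated.** A uniform effect lies wholly in the between-person direction, so it gives the 4-df test the same noncentrality, λ = 3.365² = 11.32. Noncentral chi-square power with 4 df at 0.05 is 0.776. Calibrating by t with 20 per arm gives 0.800, and simulation with estimated variances gave 0.791 to 0.797. For 0.92 with 4 df, λ must be 16.45, so a uniform effect would have to be 0.5·sqrt(16.45/11.32) = 0.60. An effect that varies over the day, with the same mean, gives the 4-df test more power than this.

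**6. If the 4-df test was simulated.** The loss in step 5 does not arise, and only step 4 can apply.

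**The case against.** The 4 df, the stated purpose and the definition of the endpoint all fit the joint test; only the label does not. An analyst who ran 3 df would be going against the written degrees of freedom. This stands as far as likely intent goes, and it means one should not infer that the trial will in fact miss a uniform benefit 95% of the time. It does not remove the conflict: the label is the only name the test has, and the model lacks the term that either test needs.

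On power, a reader might infer that 0.92 is wrong, or that every DISS subscale will be judged at 0.017. The documents support neither. The multiplicity text speaks of outcome measures, includes 0.05 among its values, and could equally refer to the three secondary EMA endpoints. It names an FDR method, under which a subscale faces the strictest value only when the others fail. Nor is 0.92 a ceiling for the trial. If success means at least one of three responding subscales, the probability under Benjamini-Hochberg is 0.997 to 0.917 over correlations of 0 to 0.9. Finally, no passage says that a 1-df test was simulated. All of this stands, and it makes every power figure above conditional.

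**Conclusion.** The conflict over the primary test is an error as written and depends on no unstated input: the named interaction has 3 df, the plan gives it 4, and the term is absent from the model. Its consequence is sharp if the label is followed, with 5% detection of a benefit equal at all four times.

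The conclusion on power is narrower: 0.92 is not shown to be the power of the planned per-subscale analysis. If the FDR family is three primary subscales, the same test keeps about 0.89 to 0.92 per subscale when all respond and about 0.83 to 0.84 when one does. If the correction does not reach the primary subscales, this reduction disappears. If a 1-df comparison was simulated, the 4-df test has about 0.78 to 0.80 at 0.05 for the same uniform effect; if the 4-df test was simulated, there is no such loss. This should be fixed before unblinding, but it does not show the sample size to be inadequate.

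**What to change.** **Main Analysis.** Add Group×Time of Day to the fixed effects. Define the primary test for each subscale as the 4-df joint Wald test of Group and Group×Time of Day. Make the 3-df interaction a secondary test of whether the effect varies over the day. This keeps the plan's df and stated purpose, and Secondary Analyses inherits the correction.

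**Sample Size.** List the DISS subscales that are primary and state whether the FDR family includes them. Rerun the simulation for the 4-df test under that rule and report the result in place of 0.92, with the ICC and its source, the SD on which d is defined, the sidedness, the assumed time-of-day pattern and the number randomised.

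**Cost.** Small edits to two sections and one simulation rerun. The stated power may come out lower. Patients, visits and data collection do not change.

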### **Statistical Analysis Plan**

All statistical analyses will be performed using the intention to treat principle; all subjects enrolled and randomized will be accounted for in the final analysis in their randomized group.

#### Main Analysis

The Primary Endpoint (PE) is the between-group difference (SUV vs PBO) in each DISS subscale at four EMA time-of-day assessments (Morning, Midday, Afternoon, Evening) across the study period. Based on our current MISP, we anticipate high adherence with >80% completion of all assessments. We will fit linear mixed-effects models for each subscale, including fixed effects for Group, Time of Day, Day (1–16 continuous), age, and sex; and a random intercept for each participant. The Group×Time interaction will be evaluated using a 4-degree-of-freedom Wald test to determine whether suvorexant and placebo differ at any time of day. If needed, the generalized additive model (GAM) will be used to account for the non-linear time effects. Covariates will be limited to age and sex at birth. Multiple imputation will be implemented for missing data; to confirm the assumptions of multiple imputation that data is missing at random, we will perform sensitivity analyses.

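### The plan never dates the first bedtime pill; if it is taken on the night of Day 1, the four Day 1 surveys are pre-treatment and should serve as the EMA baseline rather than as outcomes

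*Combined protocol and SAP*

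**What the plan says.** Main Analysis defines the primary endpoint as the suvorexant–placebo difference in each DISS subscale "at four EMA time-of-day assessments (Morning, Midday, Afternoon, Evening) across the study period". The mixed model has "fixed effects for Group, Time of Day, Day (1–16 continuous), age, and sex", plus a random intercept per participant, and the group comparison is a 4-degree-of-freedom Wald test across the four times of day. No term or exclusion separates surveys before the first pill from those after it. The section adds: "Covariates will be limited to age and sex at birth".

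The treatment section says participants are "initiated on 10mg suvorexant (or placebo), po, qhs" and, after two days, those on active drug are "increased to 20mg for a 14-day active treatment period", making "16 nights taking a pill". It gives no study day for the first of these nights. The Design section describes a "16-day active treatment phase with intensive ambulatory monitoring". Daily Survey Completion places four surveys on each of Days 1–16, starting in the morning and spread over about 12 hours. No EMA run-in is described.

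Secondary Analyses carries the primary model over to fatigue/sleepiness, positive affect and negative affect. For diary and actigraphy sleep variables, questionnaires and cognitive tests it uses ANCOVA on baseline values, and gives power as the reason.

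**The concern.** With bedtime dosing, a survey reflects treatment only if a pill was taken on an earlier night. If the first pill is at Day 1 bedtime, all four Day 1 surveys come before any drug. They then enter the model as outcomes that treatment cannot have changed, and they pull the group difference towards zero.

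The larger loss is precision. With 20 completers per arm, most of the standard error comes from stable differences between people. A pre-treatment reading of the same subscale on the same instrument removes part of that variation. On this reading the trial already collects one, and the covariate restriction prevents its use as a covariate.

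**Working it through.** **1. When is the first pill?** Two readings fit the text.

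- *Day 1 bedtime.* Days 1–16 carry the surveys and actigraphy, and the Design section describes a 16-day treatment phase with that monitoring. The home sleep apnea test, which records a night's breathing, is headed Day 0. This makes Day 1 bedtime the likelier first pill night.
- *Night before Day 1.* Nothing excludes this. The post-assessment is headed as falling before Day 16 and must precede stopping the pill, which leans mildly this way: 16 nights from Day 0 end on the night of Day 15.
- *Secondary Analyses does not decide it.* Baseline adjustment of diary variables might suggest a pre-pill diary entry on the Day 1 morning. But the same sentence adjusts actigraphy variables, and actigraphy also starts on Day 1, so Day 1 bedtime dosing supplies no pre-pill actigraphy night.

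Steps 2, 4 and 5 assume Day 1 bedtime.

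**2. Dilution.** There are 4 × 16 = 64 scheduled surveys, of which 4 (6.25%) are on Day 1. Each time of day has 16 surveys, one of them on Day 1, so each of the four contrasts shrinks equally. With a Day trend common to both arms and balanced data, the group estimate equals the difference in all-day means; a check on 60 simulated trials agreed to rounding error. If Δ is the average effect over Days 2–16, the planned estimate targets (0 + 15Δ)/16 = 0.9375Δ. This holds whatever the effect of 10 mg relative to 20 mg.

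**3. A plausible ICC.** Sample Size states power 0.92 for d = 0.5 with 20 per arm at α = 0.05 (two-sided assumed) and gives no ICC. One measurement per person gives power of only 0.35. With 64 surveys, a person mean has variance ICC + (1 − ICC)/64.

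- 1-df test: at ICC 0.208 the variance is 0.2204, the standard error is √(2/20 × 0.2204) = 0.148, and power is Φ(0.5/0.148 − 1.96) ≈ 0.92.
- 4-df test: 0.92 is reached at ICC 0.139.

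So 0.92 can be matched only by choosing an ICC, and it is neither confirmed nor refuted. ICCs of 0.14–0.21 are the values consistent with it under this simple structure.

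**4. Gain from the Day 1 covariate, complete data.** Set total variance to 1 and let s be the person-day share (assumed 0 to 0.2).

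- Planned 16-day mean: V₁₆ = ICC + s/16 + (1 − ICC − s)/64
- Days 2–16 mean: V₁₅ = ICC + s/15 + (1 − ICC − s)/60
- Day 1 mean: V_b = ICC + s + (1 − ICC − s)/4
- Standard-error ratio: √[(V₁₅ − ICC²/V_b)/V₁₆]

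| ICC 0.14 | V₁₆ | V₁₅ | V_b | Ratio |
|---|---|---|---|---|
| s = 0 | 0.1534 | 0.1543 | 0.3550 | √(0.0991/0.1534) = 0.80 |
| s = 0.2 | 0.1628 | 0.1643 | 0.5050 | √(0.1255/0.1628) = 0.88 |

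**5. Allowing for missed surveys.** The plan says "we anticipate high adherence with >80% completion of all assessments". Simulation with 20 per arm, 80% completion and person-level ANCOVA includes the cost of estimating the covariate slope. It gives these approximate reductions in the standard error of the average group difference:

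| ICC (assumed) | s = 0.2 | s = 0 |
|---|---|---|
| 0.10 | 4% | 10% |
| 0.14 | 8% | 15% |
| 0.20 | 13% | 22% |

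The gain grows with the ICC.

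**The case against.** The strongest reply is that the defect is conditional. If the first pill is on the night before Day 1, no survey is pre-treatment, and averaging over all 16 days is a legitimate intention-to-treat estimate of the regimen. That stands, and it is why the first request is for a date.

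It is also fair that an unadjusted randomised comparison is valid, that limiting covariates is a prespecified choice, and that questionnaires and cognitive tests have a Day 0 measurement while EMA has no designated baseline. The difference between the primary and secondary approaches is therefore not in itself a contradiction. What remains is that, if Day 1 is pre-pill, an EMA baseline exists, and the plan's own reason for ANCOVA applies to it.

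A reader might infer more than the documents support:

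- *Power falls below 0.92.* Not shown. The d of 0.5 may already be an average over the whole period, and the ICC behind 0.92 is not given.
- *Dilution of up to 19%.* That figure adds the 10 mg days and assumes 10 mg does nothing. The documents do not compare the doses, and those days belong to the regimen being tested.
- *Halving of the standard error.* A 54% reduction needs an ICC of 0.5, complete surveys and no day-level clustering. That ICC is far above those that match the stated power.
- *Day 1 must never be modelled as an outcome.* A longitudinal model that constrains the arms to equal means on Day 1 is an acceptable use of it.

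**Conclusion.** The point holds conditionally. What the documents establish is that the first pill is undated and that every Day 1–16 survey is an outcome. If the first pill is at Day 1 bedtime, the estimate is 15/16 of the post-pill effect, assuming completion is similar across days. That bias is small, runs towards no difference and does not increase false positives.

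The more useful consequence is the unused baseline, worth roughly 4–22% of the standard error over ICCs of 0.10–0.20. This range rests on an assumed ICC, an assumed person-day share of 0–0.2 and a correlation between people's readings that does not fade over the 16 days; it would be smaller if that correlation fades. Near the ICCs that match the stated power the gain is real but modest. Because it comes from data already being collected, the point is more than a request for missing detail.

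**What to change.** 1. In the treatment section, state the study-day bedtime of the first pill. No dosing change is needed.
2. If Day 1 precedes that pill, revise Main Analysis so that outcomes are Days 2–16, on the same calendar days in both arms and for all randomised participants. Add each participant's mean of the available Day 1 surveys for that subscale as a covariate, and amend the covariate sentence to age, sex at birth and Day 1 subscale mean. Alternatively, keep Day 1 in a baseline-constrained longitudinal model with equal group means on that day.
3. Apply the same change to the secondary EMA endpoints.
4. If the first pill is on the night before Day 1, leave the model as it is.

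The cost is wording, with no added visits, surveys or participants. Using 15 rather than 16 outcome days raises the standard error, before any covariate gain, by 0.3–0.5% at ICC 0.14 (√(0.1543/0.1534) and √(0.1643/0.1628)). The covariate uses one degree of freedom, about √(1 + 1/36) − 1 = 1.4% with 40 people, already counted in the simulated gains. At 80% independent completion, 0.2⁴ = 0.16% of participants would have no Day 1 survey, and the planned multiple imputation covers them. A separate estimate for the days after the step-up to 20 mg is optional and not part of this fix.
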